- To assume responsibility for the proper conduct of the study and not to deviate from the procedures described in the protocol.
- I am thoroughly familiar with the investigational product(s) as described in the protocol, Investigator's Brochure and any other relevant information sources provided to me.
- I am aware of and will conduct the study in compliance with the protocol, ICH GCP guidelines and all applicable regulatory requirements.
- I agree to permit monitoring and auditing of the study by the Sponsor and its designates, and inspection by appropriate regulatory authority (ies).
- I agree to ensure that all persons assisting with the conduct of the study are properly qualified for their function.

Investigator Name & Signature:

Principal Investigator: [name] Print/Type Name

Signed: _____

Signature

[figure not shown]
Date:

PROTOCOL SUMMARY

Title:	A Prospective, Multicenter, Randomized, Triple-Blinded, Placebo-
	Controlled study of IL-1RA Treatment in Patients with Acute ACL
	Tear and Painful Effusions
Précis: Objectives:	This study aims to establish efficacy and timing of administration, to reduce post-injury pain, decrease inflammatory biomarkers in ACL injured patients undergoing ACL reconstruction and correlate function, patient reported outcomes and MRI findings at 1 years after ACL injury. The study population will include 40 subjects, ages 14-40 who will be randomized into 2 groups (20 subjects per group). 1. Test the efficacy of a treatment protocol using IL-1ra and knee arthrocentesis to alleviate inflammation related knee pain and improve patient-reported outcomes (PRO) following ACL rupture. 2. Determine if intra-articular IL-1ra therapy improves levels of a panel of inflammatory, meniscus and cartilage metabolism, and oxidative stress biomarkers as measured in synovial fluid, serum and urine from patients immediately after ACL injury (baseline, 2 weeks
	after injury and at 1 and 2 years after surgery).3. Answer the question if MRI T1rho changes correlate with synovial biomarker levels and show predictive value for the overall subject patient outcome at 2 years.
Endpoint	Primary endpoint : Change in Patient reported outcomes as measured by KOOS- Symptoms
	Secondary endpoints: KOOS QOL, KOOS-pain, KOOS-Sports/Rec, Biomarker levels in synovial fluid, serum and urine at time of surgery MRI T1rho changes at 2 years
	Study Stopping Criteria
	 Local intolerance of the administered Anakinra (Kineret®) or any sign of allergic response. Development of signs and symptoms before the second time point preventing the second administration of the study drug. Any patient reported and drug related SAE after the first or second administration of the study drug. Diagnosis with any condition as outlined in the exclusion criteria during the course of the initial 2 weeks of study enrollment.
Population:	The study population will include up to 40 subjects within 28 days following of injury. The study is open to male and female participants who are between the ages of 14 and 40, who have ACL tears. Participants will be enrolled at the University of Kentucky.

Phase:	2
Number of Sites enrolling	1 (University of Kentucky)
participants:	
Description of Study	IL-1ra (Kineret®, anakinra), supplied by Sobi Pharmaceuticals, is a
Agent :	recombinant, nonglycosylated form of human interleukin-1 receptor antagonist (IL-1Ra). Kineret® consists of 153 amino acids and has a molecular weight of 17.3 kilodaltons. It is produced by recombinant DNA technology using an E coli bacterial expression system. It is available as pre-filled syringes (100 mg in 0.67 mls) and is FDA approved for daily subcutaneous injection (100 mg/day) for treatment of rheumatoid arthritis (age > 10). A total of 1.5 ml (150 mg) will be injected intra-articularly after synovial fluid aspiration 'to dryness' once between 1 and 28 days after ACL injury.
Study Duration:	24-36 months
Participant	2 years
Duration:	•

SCHEMATIC OF STUDY DESIGN

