2.2 RATIONALE

We hypothesize that IL-1Ra administered intra-articularly during the early phase of acute ACL injury will provide symptomatic pain relief and decrease synovial fluid inflammatory and cartilage degradation markers. ACL injury produces high levels of inflammatory mediators, including as IL-1, which mediate knee pain, perpetuate synovitis, and decrease functional recovery post injury and post-surgically. We have designed a clinical trial that specifically tests the ability of IL-1ra to alleviate pain following acute ACL injury and potentially changes patient reported outcomes at 2 years.

A total of 1 mL (150 mg) will be injected intra-articularly after synovial fluid aspiration 'to dryness' once at study entry 1-28 days after injury depending on time of presentation).

Rational for including pediatric population

The specific reason for enrolling the age group of children aged 14-18 is that these children have a musculoskeletal physiology like adults.

- Their major growth plates are closed.
- These patients may be treated surgically like adult patients with exactly the same surgical preparation, technique and rehabilitation as adults.
- Children, particularly girls, between the ages of 14 and 18 have the highest statistical risk in any population of tearing their Anterior Cruciate Ligament. ^{25,45}
- Children in this age group are particularly vulnerable to the later development of osteoarthritis. Lohmander et al showed that young female soccer players in this age group developed symptomatic knee Osteoarthritis secondary to the ACL injury within 12 years of the injury.²⁴ One could therefore argue that particularly children between completed puberty and 18 years of age have to be the patients requiring most of our concern regarding development of OA.
- *Furman et al.* showed that early post-injury administration of IL-1Ra did not alter bone morphology or fracture healing after intra-articular fracture but significantly reduced cartilage degradation and inflammation.⁽⁴⁶⁾
- The value of intraarticular IL-1 blockade when given immediately after intraarticular injury has been demonstrated repeatedly. In a recent publication of *Genemaras et al.* the early administration of IL-1Ra could be shown to significantly down-regulate proinflammatory Il1-β, TNF-α) and chondrodegredatory markers (MMP-3,ADAMTS-4,ADAMTS-5) immediately after non-destructive chondral impact injury to porcine articular cartilage⁽⁴⁵⁾.

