6.1.4 PREPARATION

The study drug will be kept in a temperature controlled environment according to the manufacturer's recommendations

Under aseptic clean conditions, a total of 200 mg (1.34 mL) of Kineret® (concentration 100mg/0.67ml) will be injected from 2 sterile original prefilled 100 mg syringes of Kineret into a sterile vial. A sterile graduated 5 mL syringe will then be used to draw 150 mg (1 mL) of Kineret for intraarticular injection into the knee. The medication must be transferred from the original prefilled Kineret syringes as the needles are intended for subcutaneous delivery and are not adequate for intra-articular knee injection. No dilution of the medication will be performed.

For the placebo we will utilize 1 mL of 0.9%NACL sterile saline solution drawn up in the same type of syringe as for the Kineret administration in order to maintain double blinding of the study investigator and patients.

The number of study syringes prepared by the designated research personnel or research pharmacist, per day, will depend on the number of potential enrollees or return patients requiring Kineret® injections that day.

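### Injection volume, number of doses, number of groups, synovial time points and the SAE stopping criterion are stated inconsistently in a one-dose, two-arm trial; one wording amendment would settle them

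*Combined protocol and SAP*

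**What the plan says.** **Volume.** The Protocol Summary (Description of Study Agent) says: "A total of 1.5 ml (150 mg) will be injected intra-articularly after synovial fluid aspiration". Section 2.2 says: "A total of 1 mL (150 mg) will be injected intra-articularly after synovial fluid aspiration". Section 6.1.4 sets out the preparation: "a total of 200 mg (1.34 mL) of Kineret® (concentration 100mg/0.67ml) will be injected from 2 sterile original prefilled 100 mg syringes"; the preparer is then to "draw 150 mg (1 mL) of Kineret for intraarticular injection into the knee". It adds: "No dilution of the medication will be performed". On the control it says: "For the placebo we will utilize 1 mL of 0.9%NACL sterile saline solution".

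**Doses.** The Summary has the injection given "once between 1 and 28 days after ACL injury". Section 2.2 also describes one injection at study entry, and the schedule of events (7.3.2) marks administration at Visit 1 only. Yet the Summary's stopping criteria include: "Any patient reported and drug related SAE after the first or second administration of the study drug". Sections 8.5 and 10.1.2 repeat the reference to a second administration, and 2.3.1 says the dosing was raised from one injection to two.

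**Groups and time points.** Sections 4.1, 6.1.5 and 10.2.1 define two arms. Sections 7.3.1, 10.1.1 and 10.2.1 also refer to three groups. The same sentence in 10.1.1 plans to compare synovial fluid at five time points, using a Wilcoxon signed-rank test with Hochberg correction.

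**SAE criterion.** The Summary and 8.5 require the SAE to be drug related. The copy in 10.1.2 carries no such condition.

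**The concern.** Dose volume, randomization, the synovial analysis and the stopping criteria are all operative content, and for each of them the document gives two answers.

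- Someone preparing a syringe from the Summary would read a volume half as large again as the correct one.
- Someone weighing risk and benefit from 2.3.1 reads a justification for a two-injection regimen that the trial does not give.
- An analyst cannot carry out the synovial sentence in 10.1.1 as written. The third group and at least two of the five time points do not exist, so the comparison would have to be redefined, possibly after data are available. Section 10.1.3 is marked not applicable and offers no alternative.
- An SAE unrelated to the drug meets one copy of the stopping criterion and not the other two.

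**Working it through.** **1. Volume.** Inputs: 100 mg per 0.67 mL (Summary, 6.1.2, 6.1.4); target dose 150 mg; no dilution (6.1.4). Volume = dose × 0.67/100.

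- 6.1.4, two syringes: 200 × 0.67/100 = 1.34 mL. This reproduces the stated figure.
- 6.1.4 and 2.2, the dose: 150 × 0.67/100 = 1.005 mL, or about 1 mL. This also reproduces.
- Summary, 1.5 mL: this does not reproduce. The content of 1.5 mL is 1.5 × 100/0.67 = 223.9 mg, and 223.9/150 = 1.49, or +49%. It is also 1.5 − 1.34 = 0.16 mL more than the two syringes supply.
- For 1.5 mL to hold 150 mg, the concentration would have to be 150/1.5 = 100 mg/mL. That would need dilution, which 6.1.4 rules out, and 6.1.4 sets the placebo at 1 mL.

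**2. Number of doses.**

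| Status | Where |
|---|---|
| One dose | Summary (study agent), 2.2, 7.3.2 schedule (Visit 1 only) |
| Second dose explicit (4) | Summary stopping criteria, 2.3.1, 8.5, 10.1.2 |
| Second dose only implied (2) | 6.1.4 (patients coming back for injections), 7.3.1 (the Visit 1 dose called the first) |

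**3. Number of groups.** Two are defined in 4.1, 6.1.5 and 10.2.1. Three are mentioned in 7.3.1, 10.1.1 and 10.2.1. Section 10.2.1 contradicts itself: it announces three and lists two.

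**4. Synovial time points.** The schedule marks biomarkers at Visits 1, 2, 3, 5 and 6, which is five visits. Visits 5 and 6 are restricted to serum and urine (7.3.1; 7.3.2, footnote d), so synovial visits number at most 5 − 2 = 3.

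- Visit 1: aspiration comes before the injection (7.2.1, 7.3.1), so this is a baseline sample.
- Visit 2: omitted for participants who do not have surgery (footnote a).
- Visit 3: only after elected surgery and if the knee holds fluid (footnote h).

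At most 3 − 1 = 2 synovial samples are therefore post-treatment. A participant without surgery contributes the baseline sample alone. The three arthrocenteses mentioned in 2.3.1 agree with the maximum of three.

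Two other places do not fit the schedule. The biomarker objective (Summary and section 3) lists synovial fluid alongside serum and urine, with sampling times that include 1 and 2 years, so it can be read as promising synovial fluid then. Section 7.1.1 words the Visit 3 aspiration as unconditional.

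**5. Test.** The signed-rank test is for paired data; drug and placebo participants are independent. The name printed in 10.1.1 runs signed-rank and rank-sum together. Section 2.1 uses the same name for the pilot trial, where significance is reported within the treated group, which is a paired use. The unpaired rank-sum test is the rank test for the comparison between groups.

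**6. SAE criterion.** Drug-relatedness is required in two of three copies (Summary, 8.5) and absent from one (10.1.2).

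**The case against.** The best defence is that the sections people act on are correct. Every dosing statement gives 150 mg, 6.1.4 has the right volume, and under 6.1.5 the investigator uses a prepared syringe matched to the patient's ID. The schedule shows one dose, the design section shows two arms, and no sample-size figure depends on any of this. On that view most of the point is editorial. This stands as a limit on the practical dosing risk. It does not rescue 10.1.1, which has no correct counterpart elsewhere, or the self-contradiction in 10.2.1.

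Several stronger readings are tempting and not supported.

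- A reader might infer that participants will be overdosed by 49%. That would require someone to prepare from the Summary and ignore 6.1.4. Nor is a cap of +33% (200 mg from the two syringes) a sound substitute: the two-syringe step sits in the same section that says 1 mL, so that figure mixes two scenarios.
- A reader might count 6.1.4 as a fifth explicit statement of a second dose. With a window of 1 to 28 days, a returning patient could be coming back for the only injection.
- A reader might infer that the Hochberg correction is fixed at five comparisons, with a strictest step of 0.05/5 = 0.010 against 0.05/3 = 0.0167 for three. Section 10.1.1 sets no family size, the procedure uses the p-values that exist, and Visit 1 is before treatment, so neither threshold follows from the text.
- A reader might conclude that 10.1.2 is simply wrong, because two copies say drug related and 5.5 refers to the criteria mentioned above it. But 5.5 is discretionary, and the narrowing of a safety criterion is for the sponsor to decide.

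**Conclusion.** The inconsistencies are real and should be fixed. The Summary volume is wrong: 1.005 mL is correct against 1.5 mL stated. A second dose is explicit in four places and implied in two. Three groups are mentioned in three sections of a two-arm trial. Five synovial time points are planned where at most three aspirations are scheduled, at most two of them post-treatment, and the named test is paired where the comparison is between groups. One of three copies of the SAE criterion differs in substance.

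The weight is uneven. The volume and second-dose text carry little practical dosing risk. The group, time-point and test wording matters most, because it cannot be executed as written. The SAE wording is a separate matter that needs a decision.

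This rests on taking the schedule of events, 4.1 and 6.1.4 as the intended design. They agree with one another on dose, arms and volume, and nothing in the remaining text describes a third arm.

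**What to change.** One amendment, wording only:

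- **Volume.** Change 1.5 mL to 1 mL in the Summary. The 1 mL placebo needs no change.
- **Doses.** State a single administration throughout: one 150 mg injection in 2.3.1; remove returning patients from the 6.1.4 sentence; call the Visit 1 dose simply the dose in 7.3.1. In the Summary, 8.5 and 10.1.2, delete the stopping bullet about events that prevent a second administration, and refer in the SAE bullet to the administration only.
- **Groups.** Change three to two in 7.3.1, 10.1.1 and 10.2.1.
- **Synovial analysis (10.1.1).** Replace the five time points with the scheduled aspirations: Visit 1 (before injection), Visit 2 (surgery participants) and Visit 3 (after surgery, if fluid is present). Name the Wilcoxon rank-sum test for the between-group comparison, and apply Hochberg to the post-treatment synovial comparisons actually made.
- **Alignment.** In the same edit, make the biomarker objective (Summary and section 3) clear that the 1- and 2-year samples are serum and urine, and make the Visit 3 aspiration in 7.1.1 conditional, as in the schedule.
- **SAE criterion.** The sponsor chooses one wording and uses it in the Summary, 8.5 and 10.1.2.

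The cost is the amendment itself. Sample size, drug supply and visits do not change.

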2 INTRODUCTION: BACKGROUND INFORMATION AND SCIENTIFIC RATIONALE

2.1 BACKGROUND INFORMATION

A majority of individuals with partial or complete rupture of the anterior cruciate ligament (ACL) develop post-traumatic osteoarthritis (PTOA) 5-15 years after the initial injury. The long-term consequences of PTOA include arthrofibrosis, pain, limited motion, and recurrent instability. Because ACL injuries occur most often in younger individuals (average age 14-29 years), pain and other debilitating symptoms occur most often during patients' most productive years costing society upwards of 3.06 billion dollars annually [1]. Current surgical and non-surgical treatment options for ACL injury, while relatively successful in restoring function and stability in the short term, do little or nothing to reduce or prevent the development of PTOA later in life.

ACL rupture, with or without accompanying damage to nearby cartilage and bone, initiates a persistent cascade of inflammation and catabolic enzyme activity leading to OA of the knee joint. We propose to disrupt the inflammation-driven cascade with recombinant Interleukin 1 receptor antagonist (IL-1ra).

IL-1ra was chosen because it is safe, well tolerated, and has been used to treat RA, juvenile inflammatory arthritis, and post-surgical persistent knee effusions as well as knee stiffness.[2-4_] Our own preliminary data suggests that IL-1ra reduces pain and improves function in patients with acute knee injury and arthrofibrosis. IL-1ra binds to the Interleukin 1 receptor and nonproductively blocks the proinflammatory and cartilage catabolic activities of Interleukin 1 alpha and beta. IL-1ra levels in synovial fluid are initially higher following acute ACL injury but vanish rather quickly. Subsequently, IL-1 β levels rise slower in joint fluid after ACL rupture and remain high for longer periods of time. IL-1ra has had mixed results in the treatment of established OA, possibly due to its short half-life in vivo. However, if given shortly after the initial inciting event potentially initiating the development of OA, the effectiveness may be significantly higher.

Unlike primary OA, which typically strikes older individuals and develops silently over the course of many years, post-traumatic OA is thought to begin at the moment of ACL injury in many individuals. Capitalizing on the expertise and experience of our collaborative team of investigators, we have chosen to seize this window of opportunity and provide the field with valuable new data regarding the importance of reduction of the initial inflammatory response to injury in acute ACL tears.

It is estimated 250,000 injuries to the anterior cruciate ligament (ACL) occur each year (1). These injuries predominantly occur at young age (14-18 years) The incidence of these injuries in Kentucky alone is 108/100.000 (2), a number that is on par with the incidence of prostate cancer in men in the US (125/100.000) and higher than lung cancer in the US (79/100.000)(2) A high-school soccer player has a knee injury risk of 1/50 player hours. In light of the fact that regardless of whether or not the ligament is reconstructed, at least 50% of these patients will develop post-traumatic osteoarthritis (PTOA) 10-20 years after injury. (3,4) The consequences of PTOA are debilitating, often resulting in participation restrictions and activity limitations that affect thousands of individuals each year. Currently the identification of treatment interventions, prevention strategies, or changes to current treatment algorithms to delay or deter the development of post-traumatic structural damage and subsequent PTOA development is limited as the precise mechanism and risk factors for the development of PTOA following ACL injury is unknown.

[figure not shown]

it much more amenable to early intervention than primary OA whose onset is not clearly definable at this time. For many years, however, it was believed that the biomechanically and anatomically correct reconstruction of the ACL would restore near normal joint kinematics. Biomechanically the knee joint can be restored to near normal knee kinematics using the latest

anatomic ACL reconstruction techniques. However, the considerable variation in response to surgical treatment even in well-controlled studies (2, 13-16) and recent systematic reviews has suggested that reconstructive surgery of the ACL or meniscus fails to protect against OA development (2,4). When abnormal joint stressors and abnormal joint physiology occur together, the outcome is potentially even more severe (Figure 2, from Lohmander et al (2)). This is illustrated by the fact that severe meniscal damage to the knee is more likely to cause eventual knee OA in patients with hand OA (evidence for a genetic predisposition to OA) compared with patients without hand OA (17).

ACL Injury and Damage to Articular Cartilage: Chondrocytes (matrix secreting cells) are pressure sensitive, and cannot survive compressive forces above a certain threshold, even if the cartilage matrix itself is not injured directly. This threshold may often be exceeded during ACL injuries. Without a sufficient number of chondrocytes to maintain a scaffold, the matrix eventually breaks down over time, causing pain and potential disability to the affected knee joint, often many years after ACL rupture. While the injury mechanism may lead to direct cartilage damage, resulting biomechanical changes of knee function such as increased rotational instability, postsurgical changes or subtle loss of range of motion may lead to progressive breakdown of articular cartilage in the medial or lateral compartment and may appear as early as 2 years after injury (18,19) as illustrated in Figure 1. Indeed, Neuman et al. (20) reported knee cartilage glycosoaminoglycans changes within 2 years after ACL injury. These changes are indicative of posttraumatic OA.

**Previous Clinical Research**: The IL-1ra drug we are planning to use has been previously utilized in this patient population. The use of this drug is advantageous as it constitutes a meaningful repurposing of an already existing drug that has been shown to be safe in this patient population.

Study 1: *IL-1Ra decreased pain in an open label trial of arthrofibrosis:* [name], Co-Investigator of this study, conducted two small clinical trials to test the beneficial effect of IL-1ra, an inhibitor of IL-1 biological activity, in vivo. Six patients who failed to meet entry criteria for a separate randomized trial because of age or time from injury to presentation, were entered into a small open label study in which they received 150 mg IL-1ra (anakinra, Amgen) intraarticularly for the treatment of acute ACL injury (n=2), or chronic, recurrent, arthrofibrosis following surgical lysis of adhesions (n=4). All 4 arthrofibrosis patients reported improvement in knee pain, swelling, and joint motion. Examination by the treating physician and by physician global assessment confirmed these results. Five out of six patients reported clinically significant pain relief after the treatment. There were no other complaints related to the drug and no evidence of significant adverse events in any patient. These results corroborate findings from animal studies and imply that adequate exposure to IL-1Ra early in the course of disease may potentially reduce pain and stiffness (21).

Study 2: IL-1Ra decreased pain, and improved function, and lowered IL-1 α levels in synovial fluid in a randomized pilot trial of ACL rupture: In a second randomized trial, 11 patients with isolated ACL tears scheduled for later ACL surgery were treated with 150 mg (anakinra, Amgen; 6 patients) or equal volume saline placebo (5 patients) intra-articularly within the first 30 days of acute knee injury. Mean age of participants was 24 ± 4 (SD) years, (6 male, 5 female). Enrollment was limited to patients under 40 years of age to try to insure the lack of underlying pre-existing arthropathy. Patients were recruited a mean 15 ± 7 (SD) days from injury (range 6-27 days). Self-report of pain on a Likert scale 0-10 was recorded at baseline (0), 4 days, 14 days, and 28 days after treatment as well as on the day of surgery. The standardized KOOS and IKDC questionnaires were also obtained.

Using the non-parametric Wilcoxon signed-rank sum test, significant differences (p<0.05) were observed in the anakinra treated group only: Pain was reduced in the anakinra treated group of patients by 23% after 4 days, improvement in Activities of Daily Living by 46%, and improvement in total KOOS by 24%; in contrast the placebo group improved by only 4%, 6% and 7% for these outcomes, respectively. This suggests a significant early effect in this patient population that is beneficial for the early rehab process prior to surgery(22).

Synovial fluid IL-1 α decreased over 1 month in response to a single IL-1Ra intra-articular injection in our pilot trial. The change with treatment (Day 0 to Day 28) in synovial fluid IL-1 α constituted the most intriguing and promising cytokine result from this pilot trial. IL-1 α increased in all the placebo treated patients (n=4 pairs of samples available); whereas IL-1 α decreased in 4 or 5 of the anakinra treated patients (n=5 pairs of samples available)(21).

Study 3: In order to prove that we have the ability to perform a high level (GCP) randomized clinical trial our group has performed a randomized clinical trial involving ACL patients in the same study design featuring identical enrollment (inclusion/exclusion) criteria as the one proposed in this contract (MOON-AAA Clinicaltrials.gov identifier: NCT01692756). In this multicenter early intervention trial testing the effect of Triamcinolone administration patients underwent knee joint aspirations, blood draws and urine collections at three time points prior to ACL surgery.

Table 1: Enrollment data MOON-AAA trial						
	range mean					
AGE	13-33	18.58				
M:F	Male: 25	Female: 18				
BMI	19.1-31.6	24.25				
t visit 1	1-8	4.17				
t visit 2	7-20	11.53				
t surgery	10-51	28.94				

PRO's and clinical exams were performed at all time points prior to surgery and at 4 time points post-surgery up to 6 months post-surgery. We have successfully enrolled 3-4 patients per month in the last 12 months actually exceeding the goal of 2 patients / month as initially estimated. The average time from injury to enrollment is 4.2 days with an average patient age of 18.6 years. No patients have been lost to follow-up. This trial has just completed enrollment and is in the process of data analysis (see table 1). This trial has been extraordinarily successful and was able to show that the initial chondrodegradatory response, as measured in synovial fluid can be modified intraarticularly with the administration of triamcinolone acetonide.

Pediatric dosing - Kineret®, was studied in a single randomized, blinded multi-center trial in 86 patients with polyarticular course Juvenile Rheumatoid Arthritis (JRA; ages 2-17 years) receiving a dose of 1 mg/kg subcutaneously daily, up to a maximum dose of 100 mg. The 50 patients who achieved a clinical response after a 12-week open-label run-in were randomized to Kineret® (25 patients) or placebo (25 patients), administered daily for an additional 16 weeks.

A subset of these patients continued open-label treatment with Kineret® for up to 1 year in a companion extension study. An adverse event profile similar to that seen in adult RA patients was observed in these studies. Pediatric use of Kineret® was not recommended due to difficulty dosing the medication in smaller children requiring less than 100mg per dose and because efficacy could not be demonstrated due to low trial enrollment. No safety issues were seen. The dosing problem will not come to bear in our patient population as we only enroll children 14 years and older.

Trial Registration Number: NCT00339157. First prospective placebo controlled trial to evaluate the effectiveness of IL-1Ra for SJIA. Enrolled a total of 24 patients: mean (SD) age of 9.5 (5) years; female subjects entering the study were prepubescent, sexually inactive or required to use

effective contraception; 12 received 2 mg/kg sc daily for 1 year; 10 received placebo for one month then 2 mg/kg sc daily for 11 months. Max dose 100 mg qd. Anakinra treatment was effective in SJIA. They noted in the Discussion that: " PK data suggested that low-weight children might have benefited from a higher anakinra dosage."

